### 3.2 Recruitment, screening and informed consent procedure

Participants are recruited through the professional network of the researchers involved. Consecutive ongoing recruitment will take place at the ZHAW through the physiotherapists at the in the Departement of Health Science. A general notice about the study and possibility to participate will also be placed in surrounding fitness centres.

All participants can freely decide to participate in this project, and it will be ensured that there is no dependency between participants and research staff. If an individual expresses interest in participating in this study, a visit to the strength training facilities at the ZHAW will be scheduled via email or phone. During the first visit, the lead investigator will explain to each participant the nature of the study, its purpose, the procedures involved, the expected duration, the potential risks and benefits and any discomfort it may entail. Each participant will be informed that the participation in this study is voluntary and that she/he may withdraw from the study at any time without negative effects.

All participants will be provided a participant information sheet and a consent form describing the study and providing sufficient information for participants to make an informed decision about taking part in this study. Inclusion and exclusion criteria will be clarified by asking potential participants for self-declaration. Participants can ask questions and ample time for consideration will be given to each participant to decide whether to participate or not. A pregnancy test will be scheduled for female participants prior to being considered for additional MRI data acquisition.

The formal consent of a participant, using the approved consent form, will be obtained before the participant is submitted to any study procedure. The consent form will be signed and dated by the investigator or his designee at the same time as the participant signs the form. A copy of the signed informed consent form will be given to the study participant. The consent form will be retained as part of the study records. Participants do not obtain any compensation besides the travel costs.

### 3.3 Study procedures

Project start: May 2021

Project end: May 2025

The overall plan of this 4-year project is given in Table 3.3.1; the schedule of assessment is given in Table 3.3.2; and a summary of all project visits in Table 3.3.3, respectively.

The study protocol consists of three phases, including three visits to the research and training facilities of the ZHAW for all participants, as well as an additional visit to the MRI facilities of the SCMI for a sub-group of 12 participants. The total duration of the study-related visits is 9 hours for  $n=36$ , and an additional 0.5h for the 12 participants who are scheduled for MRI.

#### PHASE A: Screening, informed consent & baseline measurements.

- **1st Visit:** Screening, informed consent, health- and training-related questionnaire, allocation into three study groups (Group#1: no training, Group#2: 1 training per week, Group#3: 3 trainings per week). The approximate duration of the 1st Visit is **1h**.
- **2nd Visit:** Baseline measurements. 3D body surface scan, anthropometric measurements, ultrasound, isokinetic strength tests, iPhone/watchOS measurements and optical motion capture during exercise execution. The approximate duration of the 2nd Visit is **4h**. The time between the 1st and 2nd visit is defined within two weeks of the 1st visit to fit in with the participant's schedule.
- **MRI scan** (sub-group,  $n=12$ ): An additional visit is scheduled for the sub-group of  $n=12$  participants to obtain data from MRI of the lower limbs. The scan time is 10-15 minutes, with the total duration of the visit to the MRI facilities at the SCMI being approximately **30**

**minutes.** MRI data acquisition is individually defined within two weeks of the 1st visit to fit in with the participant's schedule.

PHASE B: 8-week strength training intervention. Conduct of an 8-week strength training intervention of key muscle-tendon groups associated with knee joint stability in the training-specific setting of each participant. Participants are randomly allocated into three study groups with increasing levels of loading (Group#1: no training, Group#2: 1 training per week, Group#3: 3 trainings per week) with the same number of subjects and gender distribution in each group ( $n=12$  per group, 6F and 6M). The same guidelines for the warm-up and the type of exercises will be given prior to the intervention study to each participant. Participants are asked to record exercise load and volume as well as monitor training-related variables and 1RM using the *iOS Strength Control app*. Participants perform the strength training self-directedly in their chosen fitness/training facilities as it fits into their weekly routine. Contact to the study investigator is ensured at all times in case of questions.

PHASE C: Post-intervention measurements.

- **3rd Visit:** The same measurements as at baseline (2nd Visit) will be taken after the strength training intervention, following the same protocols so that the key outcome parameters can be compared before/after training. The approximate duration of the 2nd Visit is **4h**. The 3rd visit is defined within 7 days following the 8-week strength training intervention.

All the procedures in this study are standard procedures in athlete performance monitoring and musculoskeletal health & sports science. 3D body surface data are taken with the participant standing in neutral standing position using a structured light body surface scanner at the ZHAW, taking only a few seconds with extremely high accuracy between the scanned and the actual body volume without requiring any physical contact [37]. Strong in-house support is provided by the department of physiotherapy, at the ZHAW for access and expertise with isokinetic tests, ultrasound and anthropometric measurements according to ISAK standards. Kinematic data will be recorded simultaneously from the iPhone/watchOS and synchronised to a 3D motion capture system (10 camera Vicon System, Oxford Metrics Group, UK). A laptop is used that connects via Bluetooth with the mobile measurement devices, and has the required software for data acquisition and analysis [33]. The set of exercises are standard exercises for strength training, and instructions are given according to established guidelines (see Table 3.3.2). The order of exercises and 3-minute rest interval between exercises are defined to minimise the effects of muscular fatigue on the study results.

MRI scans from pelvis to the toe with the participants lying supine with straight legs are done at the SCMI with support from a professional radiographer (facilities, including technical support are booked by hour) in line with previous research by our group [21] (Scan parameters: TR-TR-3690 ms, TE-67 ms, Slice thickness 4 mm, base resolution 320, gap between slices 10 mm, approximately 70 pictures, 6.5 s per picture). The total scan time is approximately 10-15 min. The chosen values of 4 mm for slices thickness and 10 mm gap between slices are the minimum number of images possible to ensure sufficient images for deriving subject-specific muscle-tendon lengths and volumes of each participant.

Derivation of muscle volume and CSA based on MRI and computational modelling will be done using the open-source modelling environment OpenCMISS ([www.opencmis.org](http://www.opencmis.org)). OpenCMISS is an interactive computational modelling environment for Continuum Mechanics, Image analysis, Signal processing, and System identification, which has extensively been used for high-order subject-specific modelling of the musculoskeletal system. It provides generic model libraries, numerical algorithms and image processing tools for anatomically-based modelling and biomechanical analysis of muscle-tendon deformation [20-22]. Thereby, the present study will extend on previous efforts to derive muscle volume using the HMF technique by adjusting the HMF objective function to incorporate subject-specific thickness of the skin layer based on anthropometric measurements, as well as better matching of the generic musculoskeletal model to the target population group (i.e. age group and gender). For validation purposes, muscle

boundary surfaces will be manually segmented from the MRI data and muscle volumes will be derived by performing numerical quadrature over the parameterised muscle boundary surfaces. The resulting muscle volumes of hamstrings, quadriceps and triceps surae will be compared between MRI and the fitted results from HMF; while data from ultrasound will provide means to validate the accuracy of the predicted adaptation in CSA of hamstrings and quadriceps due to the strength training intervention.

Digital data is safely stored on the secured server architecture at the ZHAW with restricted access to study staff only (see also Section 7). Collected material, including signed consent forms and participant identification list, are safely stored at the ZHAW in locked cabinets. Expected biases to the project include gender, subject-specific training expertise and skin marker artefacts during optical motion capture. The sample size and population group are specified to allow the analysis of gender-specific differences on study results. Thereby, the inclusion/exclusion criteria and study protocol, including a training-related questionnaire, are defined to minimize the bias of training experience; and the functional calibration procedure, that will be employed in this study for optical motion capture, has been shown to minimise the effect of skin marker artefacts on kinematic analysis results [15, 48].

**Table 3.3.1.** Overall project plan, starting in first quarter of year 1 (May 2021)

	YEAR 1				YEAR 2				YEAR 3				YEAR 4			
Technology set-up and preparation																
Recruitment																
Data acquisition																
Data analysis																
Project management & reporting																

**Table 3.3.2.** Schedule of assessments

Time (weeks)	>-1 day	0	0-2	0-2	8-10
Goal	Info	Screening	Baseline	MRI	Post-intervention
Oral and written information	+				
Check inclusion-/exclusion criteria		+	+		+
Written consent		+			
Participant characteristics		+			
Health- & training-related questionnaire		+			
Anthropometric measurements ISAK			+		+
3D body surface scan			+		+
Ultrasound measurements			+		+
Isokinetic strength tests			+		+
iPhone/watchOS			+		+
Optical motion capture			+		+
MRI				+	(n=12)

**Table 3.3.3.** Summary table listing all project visits, duration, measurements, procedures and instructions to the participants.

TIME	MEASUREMENT	PROCEDURE/EXERCISE	INSTRUCTIONS
1 st Visit: Screening & informed consent (n=36)			

1 h	Informed consent Health- and training-related questionnaire	Inform about study protocol in detail, answer questions, check inclusion and exclusion criteria, assign participant ID, fill in health- and training-related questionnaire.	Participant to carefully read through informed consent and take time for questions and consideration to participate in this study. Participant to fill out consent form and questionnaire.
2nd Visit and 3rd Visit: Baseline measurements & post-intervention measurements (n=36)			
4h	Welcome	Outline procedure and double-check inclusion/exclusion criteria. Withdraw participant if health situation has changed.	Participant self-declares inclusion/exclusion criteria.
	Anthropometric data	Anthropometric measurements according to ISAK standards. 3D body surface scan in relaxed neutral position and image capture from frontal and lateral. Ultrasound of hamstrings and quadriceps according to established protocols at the Swiss Olympic Medical Centre	Participants to stand upright on marked location in relaxed neutral position. 3D body surface scan takes 5-10minutes. The participant is asked to stay as still as possible. Participants to sit upright with their lower limbs relaxed and supported in extended position.
	Warm up	Preparation for strength assessment and kinematic data acquisition	Participant performing individual warm up of 5-10 minutes on rower or bike.
	Isokinetic tests	Isokinetic tests according to established protocols at the Swiss Olympic Medical Centre.	Participants performs the standard isokinetic test for hamstring and quadriceps on a commercial testing machine.
	Functional calibration	Measurement set-up and conduct of functional calibration and synchronisation of Apple Watch, iPhone and Vicon system.	Participant to stand upright in relaxed neutral position for attachment of reflective skin markers and Apple watch. Participant to perform set of standard movements for functional calibration.
	Exercises for the assessment of strength- and training-specific data	Forward lunges	Participant to stand upright and move into a lunge position with the front leg. Keep back straight and head upright. Initiate upward movement before the rear knee touches the ground [43].
		Side lunges	Participant to stand upright and move into a side lunge position. Keep back straight and head upright. Shift weight back into neutral standing position and alternate to other side.
		Squat	Participant to stand upright with feet hip-width apart and slightly pointing out. Make sure not to bend forward but keep back straight and knees pointing out in direction of toes.
		Drop jumps	Participants jump from a 30cm box onto the ground and stand still after landing [41].
		Counter-movement jumps	Participant to stand upright, dynamically move into a squat position followed by a vertical jump as high as possible.
		Side-step cutting movements	Participants sprints forward and changes the direction with a cutting side step to the left respectively the right side.
	Dismissal	Participant is shown preliminary results and is informed about further research process.	Participant is given time to look at data and ask questions. Outlining of further study process and thank you for participation.
4rd Visit: MRI of the lower limbs (n=12)			

0.5 h	Welcome	Outline procedure and double-check inclusion/exclusion criteria. Pregnancy test for female participants. Withdraw participant if health situation has changed.	Confirm inclusion/exclusion criteria and time for questions.
	MRI data	Scan to be taken at the SCMI Balgrist Campus Zurich using the 7T Magnetom Terra (Siemens) that can be booked per hour, including imaging support through a professional radiographer.	Participant asked to lie on her/his back on bed which is slid into the scanner. Asked to lie as still as possible during the scan (approx. 10min). Participant in voice contact with radiographer at all times and emergency button in reachable distance to stop the scan immediately should participant feel uncomfortable.
	Dismissal	Participant is shown preliminary results and is informed about further research process.	Participant is given time to look at data and ask questions. Outlining of further study process and thank you for participation.

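### Allocation is listed at Visit 1, before the effort-dependent baseline tests at Visit 2, and the protocol does not say that the group is withheld until baseline is complete

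*Combined protocol and SAP*

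**What the plan says.** Section 3.3, Phase A, places allocation in the 1st Visit: "Screening, informed consent, health- and training-related questionnaire, allocation into three study groups". The 2nd Visit holds the baseline measurements, among them "ultrasound, isokinetic strength tests, iPhone/watchOS measurements and optical motion capture during exercise execution". On the gap, Phase A states: "The time between the 1st and 2nd visit is defined within two weeks of the 1st visit". Table 3.3.3 describes the strength test at the 2nd and 3rd Visits: "Participants performs the standard isokinetic test for hamstring and quadriceps on a commercial testing machine".

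Three other places bear on timing:

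- Phase B, which follows the baseline phase, describes allocation again without a date: "Participants are randomly allocated into three study groups with increasing levels of loading".
- The 1st Visit row of Table 3.3.3 reads "Inform about study protocol in detail, answer questions, check inclusion and exclusion criteria, assign participant ID" and goes on to the questionnaire. It mentions neither allocation nor telling participants their group.
- The schedule of assessments (Table 3.3.2) has no allocation row.

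Section 2.2 makes change in 1RM and H:Q ratio the primary endpoint and says it will be compared between the three groups. Section 3.3 lists the biases the investigators foresee: "Expected biases to the project include gender, subject-specific training expertise and skin marker artefacts during optical motion capture". Knowledge of the allocated group is not among them. The document describes no allocation concealment and no blinding of participants or assessors.

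**The concern.** Baseline should be measured before the assigned group can influence it. The only text that ties allocation to a visit puts it first, with up to two weeks before the baseline tests. That is a quarter of the length of the 8-week intervention (2/8 = 0.25).

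This population has room to react. Section 3.1 describes people who already do weekly strength training, and one arm is asked not to train. A participant who knows the group could stop, train ahead, start early, or push more or less hard in the baseline test. Section 1.3 defines 1RM as the most a person can lift through the full range, so it depends on effort.

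Any such shift that differs by group goes straight into the change score. Adjusting for baseline does not reliably remove it, because baseline would itself have been affected by allocation. Section 4.1 names no separate model for the between-group comparison, so nothing there addresses the problem.

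A smaller point goes with this. Eligibility is checked again at the 2nd Visit, with the instruction "Withdraw participant if health situation has changed", and section 4.2 recruits further participants until 36 datasets are complete. A loss between allocation and baseline that was related to group would not show in the final 12 per group.

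**Working it through.** **1. Order of events**

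| Place | Allocation | Baseline tests |
|---|---|---|
| 3.3, Phase A | 1st Visit | 2nd Visit, up to two weeks later |
| 3.3, Phase B | described again, no date | already done |
| Table 3.3.2 | no row | weeks 0–2 |
| Table 3.3.3, 1st Visit row | not listed | 2nd Visit row |

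Read literally, Phase A has allocation before baseline. Phase B and Table 3.3.3 allow another reading. None of them says when the group is disclosed.

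**2. The plan's own figures**

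Section 3.1 gives squat 1RM of 170.6 (SD 21.4) kg before and 200.8 (SD 19.0) kg after training, d = 1.5, alpha 0.025, power 0.9 and 11 per group.

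- Planning change: 200.8 − 170.6 = 30.2 kg.
- Pooled SD: √((21.4² + 19.0²)/2) = 20.2 kg, so d = 30.2/20.2 = 1.49, which agrees with 1.5.
- Two-sample t-test, d = 1.5, power 0.9: one-sided 0.025 gives 10.40, rounded up to 11, which matches the plan. Two-sided 0.025 gives 12.39, rounded up to 13.

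The sample size is not in dispute here, and moving allocation does not change it.

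**3. Size of a shift (illustration only)**

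The documents give no figure for a shift in baseline caused by knowing the group. Assume that one group's mean baseline moves by a fraction p of 170.6 kg and the others do not move. Then b = p × 170.6.

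| Assumed p | b (kg) | b/20.2 (SD) | b/30.2 |
|---|---|---|---|
| 0% | 0 | 0 | 0% |
| 3% | 5.1 | 0.25 | 17% |
| 5% | 8.5 | 0.42 | 28% |

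**4. Effect on a between-group test of change (illustration only)**

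The pre–post correlation r is also not given; take 0.5 to 0.9. The SD of change is √(21.4² + 19.0² − 2r × 21.4 × 19.0), which is 20.3 kg at r = 0.5 and 9.3 kg at r = 0.9. The calculation uses a two-group t-test with 12 per group, no true difference and nominal two-sided 0.025.

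- p = 0: 2.5%, as intended.
- p = 2% (3.4 kg): false-positive probability about 4% (r = 0.5) to 8% (r = 0.9).
- p = 5% (8.5 kg): about 10% (r = 0.5) to 45% (r = 0.9).

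**5. H:Q ratio**

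If hamstrings and quadriceps both fall by the same fraction, the ratio does not move: 0.95H/0.95Q = H/Q. It moves only if the two are affected unequally. For example, a 5% fall in quadriceps alone multiplies the ratio by 1/0.95 = 1.05.

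**The case against.** The strongest reply is that the mechanism needs participants to know their group before Visit 2, and no text says they do. A reader might infer from Phase A that they are told at Visit 1. The documents do not support that as fact: the 1st Visit row of Table 3.3.3 lists neither allocation nor disclosure, and Phase B describes random allocation after the baseline phase. This stands, and it limits the point to an order of events that permits early knowledge, with no stated safeguard. It does not remove the point. If the investigators mean to allocate at the start of Phase B, the Phase A text is wrong and needs the same edit.

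Second, the primary objective is prediction, and the repeated measures ANOVA in section 4.1 compares predicted with measured values. Reduced effort at one visit would tend to lower both, so that analysis is less exposed. This also stands. The exposed part is the between-group comparison of change named in section 2.2.

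Third, ultrasound and the body scan are not effort tests. They could move only through changed training in the gap. This stands.

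Fourth, the shifts used above are assumed, and they are applied to figures from 19 professional rugby league players, whereas this study enrols 18 women and 18 men with at least a year of training. This stands, so the percentages are not estimates for this trial.

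Fifth, withdrawal at the eligibility re-check is tied to a change in health, for which section 3.4 gives acute pain or injury as the example. The same check recurs at the 3rd Visit, so later allocation closes only the losses before baseline. The removal point is therefore secondary.

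**Conclusion.** The point holds as a gap in the plan. Allocation is listed before an effort-dependent baseline, withholding of the group is not stated, and the descriptions of timing do not agree. As a result, the between-group comparison of change in 1RM and H:Q ratio is not guaranteed to be unbiased.

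A reader might go further and conclude that this comparison is certainly biased, or that the whole primary endpoint is lost. Neither follows. Bias arises only if the group becomes known before Visit 2 and that knowledge shifts baseline differently by group.

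If it did, an assumed shift of 3% to 5% would be 5.1 to 8.5 kg on the planning mean, or 17% to 28% of the planning change. At zero shift there is no bias, and for H:Q ratio a proportional shift in both muscle groups cancels. The size rests entirely on assumed shifts and, for the error rates, on assumed correlations.

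This should be fixed, since analysis cannot reliably remove such a bias afterwards and the change is cheap. Confidence is moderate because early disclosure is an inference.

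**What to change.** - In section 3.3, Phase A, delete allocation from the 1st Visit.
- State that random allocation, stratified by gender, is made and disclosed only at the end of the 2nd Visit, after the eligibility re-check and all measurements of that visit.
- Make Phase A, Phase B and Table 3.3.3 say the same, and add an allocation row to Table 3.3.2.
- State how the sequence is generated and who releases it. Section 7.2 shows REDCap in use for demographics, questionnaire and anthropometric data, but nothing shows that it is set up for randomisation.

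Allocation need not wait for the MRI, because section 3.1 says that the MRI validation is analysed independently of the intervention.

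The cost is protocol wording. No visit, measurement or participant is added, and the sample size is unchanged. The drawback is that participants learn their group up to two weeks later.

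### No minimum rest is set before the measurements at Visit 2 or Visit 3, so time since the last session can differ by group; separately, the text and Table 3.3.2 disagree by a week on when Visit 3 may fall

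*Combined protocol and SAP*

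**What the plan says.** - **Visit 3.** Section 3.3, Phase C: the third "visit is defined within 7 days following the 8-week strength training intervention". No lower limit is given.
- **Visit 2 (baseline).** Section 3.3, Phase A: "The time between the 1st and 2nd visit is defined within two weeks of the 1st visit". Nothing is said about rest from training beforehand. Section 3.1 requires a standing habit of at least one strength session per week, so participants may arrive at baseline recently trained.
- **Training.** Phase B allocates the arms as "Group#1: no training, Group#2: 1 training per week, Group#3: 3 trainings per week". Session days are left open: "Participants perform the strength training self-directedly in their chosen fitness/training facilities as it fits into their weekly routine". The start of the 8 weeks relative to Visit 2 is not stated.
- **Fatigue.** Exercise order and 3-minute rests "are defined to minimise the effects of muscular fatigue on the study results", and Section 6.2 offers rest during and after measurements. All of this acts within the visit. In Table 3.3.3 the only preparation for strength testing at Visits 2 and 3 is a short warm-up.
- **Schedule table.** The time row of Table 3.3.2 reads "Time (weeks) >-1 day 0 0-2 0-2 8-10": screening at week 0, baseline and MRI at weeks 0-2, post-intervention at weeks 8-10.
- **MRI.** "MRI data acquisition is individually defined within two weeks of the" first visit. Section 3.1 places it at baseline.
- **Use of the data.** Section 2.2 compares changes in 1RM, H:Q ratio, muscle volume and CSA between the three groups. Section 4.1 tests predicted against measured values.

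**The concern.** The trial sets out to relate 8-week change to training volume. A measurement soon after a leg session may reflect that session as well as the adaptation. How often this happens depends on the arm, because the arms train 0, 1 or 3 times a week. Randomisation cannot balance a quantity that the assigned arm itself determines.

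Baseline is equally open. A Group#1 participant may come to Visit 2 shortly after an own session and to Visit 3 after 8 weeks without study training, so the two visits need not be comparable even within an arm.

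The protocol treats muscular fatigue as a threat to its results, but controls only the part that arises during the visit. Recent training is absent from the expected biases listed in Section 3.3, and Section 4.1 makes no adjustment for it. If last-session dates are not recorded, the problem cannot be examined afterwards.

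The disagreement between text and table is a different matter. It affects which Visit 3 dates count as on schedule and how long the pre/post interval may be.

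**Working it through.** **A. Visit 3 window, in weeks from screening**

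Inputs: Visit 2 on days 0-14 after Visit 1; intervention 8 weeks = 56 days; Visit 3 on days 0-7 after its end. Assumption: training starts on the day of Visit 2.

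1. The table's own figure: (0 to 2) + 8 = weeks 8-10. It is reproduced only if the 7-day allowance is left out (or if baseline is confined to the first week).
2. Both text windows in full: earliest 0 + 56 + 0 = day 56 (week 8); latest 14 + 56 + 7 = day 77 (week 11).
3. The table is exceeded when baseline delay plus Visit 3 delay is more than 14 days. Of 15 × 8 = 120 day combinations this holds in 1+2+...+7 = 28 (23%). That is a count of combinations, not a probability. Any delay before the first session moves Visit 3 later still.

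**B. Gap from last study session to Visit 3**

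Gap = (7 − day of last session in week 8) + Visit 3 delay (0-7 days). All combinations are weighted equally, which is an assumption.

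- *Group#2*, one session on any of 7 days: 7 × 8 = 56 combinations. Range 0 to 6 + 7 = 13 days; mean 3 + 3.5 = 6.5. Gap ≤ 2 days: 3+2+1 = 6, and 6/56 = 11%. Gap ≤ 3 days: 10/56 = 18%.
- *Group#3*, any 3 of 7 days: 35 × 8 = 280 combinations. The last session falls on day 7, 6, 5, 4 or 3 in 15, 10, 6, 3 and 1 of the 35 patterns. Range 0 to 4 + 7 = 11 days; mean 1 + 3.5 = 4.5. Gap ≤ 2 days: 3×15 + 2×10 + 1×6 = 71, and 71/280 = 25%. Gap ≤ 3 days: 105/280 = 38%.
- *Group#3*, no consecutive days: 10 × 8 = 80 combinations. The last session falls on day 7, 6 or 5 in 6, 3 and 1 patterns. Range 0-9 days; mean 0.5 + 3.5 = 4.0. Gap ≤ 2 days: 3×6 + 2×3 + 1×1 = 25, and 25/80 = 31%. Gap ≤ 3 days: 35/80 = 44%.
- *Group#1*: no study session, so no gap is defined.

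Per group of 12, a gap of 2 days or less means about 1.3 participants in Group#2 (12 × 0.107) and 3.0 to 3.8 in Group#3 (12 × 0.254 to 12 × 0.3125).

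Sensitivity: if Visit 3 cannot fall on the last programme day (delay 1-7), the shares at ≤ 2 days are 3/49 = 6% in Group#2, and (2×15 + 10)/245 = 16% to (2×6 + 3)/70 = 21% in Group#3. The ordering is unchanged.

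**C. Scale only**

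The documents give no carry-over size. Suppose those tested within 2 days show an acute strength deficit of 0 to 10% (assumption). The Visit 3 mean of Group#3 would then shift relative to Group#2 by at most (0.3125 − 0.107) × 10% = 2.1%. On the 200.8 kg post-training squat 1RM quoted in Section 3.1 that is about 4.1 kg, against a quoted gain of 200.8 − 170.6 = 30.2 kg. This is a shift in level at Visit 3. It is not the bias in the change, which also depends on the state at Visit 2.

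**The case against.** The strongest reply has four parts.

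1. *Much of the planned analysis is hardly touched.* Section 4.1 compares predicted with measured 1RM and H:Q ratio. The app, motion capture and isokinetic data come from the same visit, as do body scan and ultrasound, so the muscle state is largely shared. This stands. The exposure lies mainly in the group comparison of Section 2.2 and in the size of the adaptation.
2. *No bias is shown.* A reader might infer that the schedule lowers apparent strength gain and raises apparent CSA gain, most of all in Group#3. The documents do not support that. They give no deficit or swelling figure, participants have at least a year of training experience, and recent training before Visit 2 could partly cancel the effect in the pre/post change. What stands is an uncontrolled difference of unknown size and net direction.
3. *The phases already order events.* A reader might take Table 3.3.2 alone and infer a baseline-to-post interval as short as 6 weeks (8 − 2). Phases A, B and C place the full 8 weeks between the two visits, so that reading does not hold. Nor is it right to infer that the plan schedules MRI after training has begun: Section 3.1 and Phase A place it at baseline. The two-week MRI window is not tied to the first session, so one clarifying sentence is enough.
4. *Training is logged.* Participants record load and volume in Phase B, so session dates may exist. No section plans to use them, and they would not cover the period before Visit 2.

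**Conclusion.** The concern holds in a limited form, as two separate defects.

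**Time since last session.** The plan permits testing the day after a leg session, and how often this can occur follows from the assigned arm: a gap of 2 days or less in about 11% of Group#2 and 25-31% of Group#3. The percentages rest on equally likely days and on counting the last programme day as day 0; the ranges of 0-13 and 0-11 days rest only on the latter. One might read the rule as 0-7 days after the last session, but the 7 days run from the end of the programme, so the true gaps are longer and differ more between arms. Whether the group comparison is materially biased, and in which direction, cannot be determined from the documents.

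**Windows.** The text allows Visit 3 up to week 11 and the table up to week 10. This one-week inconsistency makes the permitted pre/post timing unclear. It does not cause carry-over.

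Both are worth correcting before data collection, because an unrecorded last-session date cannot be reliably recovered later.

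**What to change.** - Set one minimum interval between any lower-limb strength session (study or own) and the measurements, the same at Visit 2 and Visit 3 and in all groups. The sponsor should choose the value, short enough to fit the existing 7-day window. Do not add a common maximum: Group#1 does not train, and some Group#2 participants will have had their last session early in week 8.
- Record the date of the last lower-limb session before each visit and report the gap by group and visit. The minimum removes short gaps, but longer ones will still differ by arm.
- State when training starts after Visit 2 and anchor the Visit 3 window to the first training session, with a nominal start date for Group#1. Reconcile Phase A, Phase C and Table 3.3.2 accordingly.
- State that MRI precedes the first training session.

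Cost: wording in Section 3.3 and Table 3.3.2, one date field per visit, and slightly tighter booking of Visits 2 and 3. The sample size does not change.
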